***Please enter the Short Title you would like to use to reference the study:**

1:1 Pocket Colposcope in Kenya

* This field allows you to enter an abbreviated version of the Study Title to quickly identify this study.

Document Date: 05/03/2024

NCT04998318

Standard Research Summary

Purpose of the Study

- Objectives & hypotheses to be tested

Primary

1. Compare the performance of the Pocket colposcope to Visual Inspection with Acetic Acid (VIA) and Visual Inspection with Lugol's Iodine (VILI) for detection of precancerous lesions among HPV+ women in Kenya.
2. Determine sensitivity, specificity and positive/negative predictive values of different triage strategies for HPV+ women.

Secondary

1. Analyze patient and provider pre-exam surveys to address possible obstacles in routine cervical cancer screening and build awareness.
2. Analyze patient and provider post-exam surveys to gather their perspective on use of Pocket system.

Tertiary

1. Use the de-identified colposcopy images to test our automated algorithm named CARE. This is a retrospective analysis for modeling and development of the algorithm, not guiding clinical care. The addition of the cellphone camera images will help facilitate this algorithm.

Background & Significance

- Should support the scientific aims of the research

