The Pocket colposcope has 510k FDA clearance and has been successfully used in almost 1500 unique patients globally (Figure 1) in Duke and non-Duke protocols to date. 1056 women who are HPV-positive and planned to undergo treatment at 6 Ministry of Health-supported outpatient clinics in Kisumu County will be recruited to the study. After providing informed consent, participants will be randomized 1:1 to either standard-of-care visual inspection or colposcopy with the Pocket Colposcope (Figure 2). The women randomized to the pocket colposcope will also have a de-identified image obtained using a cellphone. This cellphone does not have access to a cellular network. We are testing out the camera quality found in an ordinary cellphone.

Figure 1: Global Pocket Colposcope enrollment

Figure 2: Pocket Colposcope

Women randomized to the standard-of-care arm will undergo VIA followed by Visual Inspection with Lugol's Iodine (VILI). Women randomized to the Pocket Colposcope arm will undergo Pocket-Assisted VIA (PA-VIA), green light imaging, and VILI using the Pocket Colposcope. Women in both arms will have biopsies taken of any suspicious lesions, or two biopsies taken in random locations if no lesions are visible. The locations of the biopsies will be based on provider impression. After their study-exams and biopsies are taken, women who are eligible for ablative treatment will be immediately treated in the clinic. Those with larger lesions or lesions concerning for invasive cancer will be referred to the local hospital for an excisional procedure. Figure 3 demonstrates the study schema in greater detail below.

Figure 3: Study Scheme

Standard-of-care arm

• *Visual Inspection with Acetic Acid (VIA):* First, the cervix should be wiped with a cotton swab to remove any preexisting mucous and/or blood. A 3-5% acetic acid solution will be applied to the cervix using a spray bottle or fox swab. After approximately 1-minute, any changes to the cervix using the naked eye will be noted. Acetic acid may be reapplied if acetowhiteening diminishes during visual inspection.

• *Visual Inspection with Lugol's Iodine (VILI):* After imaging with Acetic acid, Lugol's iodine will be applied using a fox swab noting any yellow or non-staining areas. Lesion location(s) will be noted on a clock-face diagram and used to direct biopsy if a lesion is present or random biopsies will be obtained from two quadrants in the absence of a visible lesion.

Pocket Colposcope arm

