·*Pocket-Assisted Visual Inspection with Acetic Acid (PA-VIA):* First, the cervix should be wiped with a cotton swab to remove any preexisting mucous and/or blood. A 3-5% acetic acid solution will be applied to the cervix using a spray bottle or fox swab. After approximately 1-minute, using the Pocket Colposcope any changes to the cervix will be noted. Using the Calla Health image acquisition software, both white and green images of the cervix will be captured at low-resolution. High-resolution green light images will be obtained at the provider's discretion. Acetic acid may be reapplied between white and green imaging at the provider's discretion if acetowhitening diminishes. A cellphone camera image will be obtained as well.

·*Pocket-Assisted Visual Inspection with Lugol's Iodine (PA-VILI):* After imaging with Acetic acid, Lugol's iodine will be applied using a fox swab noting any yellow or non-staining areas. Using the Pocket Colposcope, images will be acquired and used to direct biopsy if a lesion is present. Random biopsies will be obtained from two quadrants in the absence of a visible lesion. A cellphone camera image will be obtained as well.

Biopsy procedure: Biopsies will be collected and processed per the following procedures. Fade-resistant, and waterproof thermal printed QR (barcode) stickers will mark all specimen containers from patients consenting to the study. These QR codes will not have any protected health information (PHI) on them, but will be electronically registered to provide 2 unique identifiers with a secure digital database allowing study personnel with a secure digital scanning device to track and register the diagnostic findings with the patient sample to enhance quality assurance and prevent misidentification. Biopsies will be processed and diagnosed according to the standard surgical pathology procedures. Two hematoxylin and eosin (H&E)-stained slides will be processed from each biopsy. [name], pathologist at the University of Nairobi, will review each slide and give a diagnosis of negative, low-grade dysplasia (CIN-1), high-grade dysplasia (CIN-2/CIN-3), or invasive carcinoma.

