We plan to proceed with prospective enrollment of 550 subjects in the research arm only. Therefore we will no longer have possible randomization into standard of care treatment. The past and newly obtained cervical images will be used to generate the treatment algorithm as described in the objective field (tertiary).

Selection of Subjects

- List inclusion/exclusion criteria and how subjects will be identified.

The subjects will be recruited from 6 different sites in Kenya. No subjects will be recruited/enrolled at DUMC.

Selection of Subjects:

Inclusion Criteria

1. Age \geq 25 years old and \leq 65 years old
2. Sex: Female
3. Positive HPV test within past 6 months
4. HIV+ women

Exclusion Criteria

1. Pregnant women (cannot perform a cervical biopsy on a patient who is pregnant unless absolutely indicated)
2. Women with a negative HPV test
3. Patients incapable of giving informed consent
4. Women with a history of cervical cancer
5. Pelvic exam concerning for cervical cancer or cervical infection

The rationale for the pregnant women exclusion is merely based on standard of care NOT for research. As a general rule, providers do not perform cervical biopsies on pregnant patients unless absolutely needed.

Subject Recruitment and Compensation

- Describe recruitment procedures, including who will introduce the study to potential subjects. Describe how you will ensure that subject selection is equitable and all relevant demographic groups have access to study participation (per 45 CFR 46.111(a) (3)). Include information about approximately how many DUHS subjects will be recruited. If subjects are to be compensated, provide specific prorated amounts to be provided for expenses such as travel and/or lost wages, and/or for inducement to participate.

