Pocket Colposcope images will be evaluated 1) at the time of the initial exam, 2) by expert colposcopists and, 3) by our image processing algorithm [12]. Provider impression of the Pocket Colposcope images, provider impression of the standard-of-care VIA/VILI and the algorithm output will be compared against pathology. The diagnostic information gained will be used to determine the sensitivity and specificity of the algorithm. Specifically, the two-sided McNemar's test will be used to determine statistically significant differences in specificity and sensitivity for each comparison 1) VIA/VILI impression vs. Pocket-provider impression during the exam, 2) expert provider interpretation vs. Pocket--algorithm-based results post-study and 3) VIA/VILI and Pocket Colposcopy based impressions (during exam) vs. algorithm-based results (post- study) to test our hypothesis that provider based interpretation of the Pocket images and the algorithm perform significantly better than VIA/VILI, and that the automated algorithm performs comparably to an expert. To obtain a better understanding of the performance of the three tests, we will carry out a standard and weighted Kappa to look at the agreement between tests and the impact of disease severity on agreement. The literature suggests that approximately 20% of the patients from each arm will have a CIN2/3 diagnosis.

Data & Safety Monitoring

- Summarize safety concerns, and describe the methods to monitor research subjects and their data to ensure their safety, including who will monitor the data, and the frequency of such monitoring. If a data monitoring committee will be used, describe its operation, including stopping rules and frequency of review, and if it is independent of the sponsor (per 45 CFR 46.111(a) (6)).

All data will be obtained at the sites in Kenya. The Duke team will be in communication with local PIs/CRCs to ensure the images and data are uploaded correctly. Data monitoring will be conducted on a routine basis by the PI and study team as specified below in Section 13. As necessary, the PI will make source documentation and protocol data available to appropriate regulatory agencies, which may include but is not limited to the DCI Monitoring Team, the DCI Cancer Protocol Committee, the DUHS IRB, the Duke University SOM's Office of Regulatory Affairs and Quality (ORAQ) and the National Cancer Institute.

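### Each arm's own exam directs the biopsies it is scored against, so sensitivity, NPV and the Pocket vs VIA/VILI contrast depend on biopsy detection rates that the plan neither states nor varies

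*Combined protocol and SAP*

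**What the plan says.** Design & Procedures sets one biopsy rule for both arms: "Women in both arms will have biopsies taken of any suspicious lesions, or two biopsies taken in random locations if no lesions are visible". It adds: "The locations of the biopsies will be based on provider impression". In the standard-of-care arm, lesions seen with the naked eye are recorded by clock position, and these records are to be "used to direct biopsy if a lesion is present or random biopsies will be obtained from two quadrants in the absence of a visible lesion". In the Pocket arm, "images will be acquired and used to direct biopsy if a lesion is present", with the same two-quadrant random rule when nothing is seen.

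Data Analysis & Statistical Considerations then states: "Provider impression of the Pocket Colposcope images, provider impression of the standard-of-care VIA/VILI and the algorithm output will be compared against pathology". For the comparisons listed there, including VIA/VILI against the Pocket provider's impression, the two-sided "McNemar's test will be used to determine statistically significant differences in specificity and sensitivity for each comparison". That section gives no cut-off for a positive impression, no correction for imperfect biopsy and no sensitivity analysis. It expects about 20% of each arm to receive a CIN2/3 diagnosis.

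Purpose of the Study makes the comparison with VIA/VILI a primary objective, and also this: "Determine sensitivity, specificity and positive/negative predictive values of different triage strategies for HPV+ women". A later paragraph of Design & Procedures ends randomisation: "We plan to proceed with prospective enrollment of 550 subjects in the research arm only".

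**The concern.** The index exam determines the quality of its own reference standard. A woman with a visible lesion has that lesion sampled; a woman without one has two quadrants sampled at random. Disease that the exam misses is then also more likely to be missed by the biopsy, and is counted as a true negative. That raises apparent sensitivity and NPV.

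Guidance differs by arm (naked eye with a diagram, or device images), so the distortion need not be equal and need not cancel. Nothing later in the plan would reveal missed disease: women eligible for ablation are treated at the same visit, and follow-up is an adverse-event phone call. At stake are both primary objectives. An observed Pocket advantage could be partly artefact, a null result could hide a real difference, and an inflated NPV would make exam-negative women look safer than they are.

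**Working it through.** **Model.** Let s be true sensitivity, d the chance that directed biopsies find CIN2+ in a diseased test-positive woman, and r the chance that two random biopsies find it in a diseased test-negative woman. Test-positive is taken to mean that a suspicious lesion was seen, and histology at first to give no false positives. The documents give none of s, d or r; all values below are assumptions.

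**1. Direction.**
- Apparent sensitivity = s·d / [s·d + (1 − s)·r]. Equivalently, apparent odds = true odds × d/r. It is overstated exactly when r < d.
- Apparent NPV = 1 − r·(1 − true NPV). It is overstated when r < 1.
- r < d is plausible. Two of four quadrants include a one-quadrant lesion with probability 1 − 3/6 = 50%, and a two-quadrant lesion with 1 − 1/6 = 83%, before any miss within the quadrant.

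**2. Same d/r in both arms.** True 0.60 vs 0.80, d = 1:

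| r | VIA/VILI | Pocket | Gap (points) |
|---|---|---|---|
| 0.25 | 0.857 | 0.941 | 8 |
| 0.50 | 0.750 | 0.889 | 14 |
| 0.75 | 0.667 | 0.842 | 18 |

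The order is kept and the 20-point gap is distorted. It need not shrink: with d = 0.9 and r = 0.5, a true 0.30 vs 0.40 appears as 0.435 vs 0.545, or 11 points instead of 10.

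**3. Different d/r by arm.**
- Equal s = 0.60, d = 1, r = 0.50 (VIA/VILI) vs 0.25 (Pocket): 0.750 vs 0.857, a false gap of 11 points.
- Reversal of 0.60 vs 0.80: true odds are 1.5 and 4, so the VIA/VILI d/r must exceed the Pocket d/r by more than 4/1.5 = 2.67-fold.

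**4. Size of the false-gap problem.** The plan's 20% is a diagnosed rate, so true prevalence π is set to make the average diagnosed rate 20%. The figure of 528 per arm is half of the 1056 in Design & Procedures. At d = 1 the fractions of disease diagnosed are 0.6 + 0.4×0.50 = 0.80 and 0.6 + 0.4×0.25 = 0.70, so π = 0.20/0.75 = 0.267, with 112.6 and 98.6 diagnosed women. For an unpaired two-proportion test at 5%, the pooled proportion is 0.80, SE0 = √[0.16(1/112.6 + 1/98.6)] = 0.0552 and SE1 = √(0.1875/112.6 + 0.1224/98.6) = 0.0539. Rejection ≈ Φ[(0.107 − 1.96×0.0552)/0.0539] ≈ 49%. At d = 0.7 the same steps give 0.677 vs 0.808, with 114.9 and 96.3 diagnosed, and 57%. At 200 per arm (half of the 400 in Subject Recruitment and Compensation) and d = 1, the numbers diagnosed are 42.7 and 37.3, and rejection is about 22%.

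**5. NPV.** With s = 0.60, specificity 0.70, d = 1 and π = 0.20/(0.6 + 0.4r):

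| r | π | True NPV | Apparent NPV |
|---|---|---|---|
| 0.25 | 0.286 | 0.81 | 0.95 |
| 0.50 | 0.250 | 0.84 | 0.92 |
| 0.75 | 0.222 | 0.86 | 0.89 |

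**6. False-positive histology.** With rate f in disease-free test-negative women, apparent NPV = 1 − r(1 − NPV) − f·NPV. The bias changes sign at f = (1 − r)(1 − NPV)/NPV. At true NPV 0.875 that is 3.6%, 7.1% or 10.7% for r = 0.75, 0.5 or 0.25.

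**7. The alternative measure.** The proportion of randomised women who are test-positive with biopsy-proven CIN2+ is π·s·d, which contains no r. For 0.60 vs 0.80 with equal d the ratio is 1.33 whatever r is. Calibrated at r = 0.5 and 528 per arm, the proportions are 0.141 vs 0.188 (d = 1, π = 0.235), power about 54%, and 0.131 vs 0.175 (d = 0.7, π = 0.3125), power about 51%.

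**The case against.** **Every woman is biopsied.** This stands. A reader might infer that disease status is unverified in exam-negative women; the documents do not support that. The two random biopsies reduce the bias, and remove it from NPV only if they miss nothing.

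**NPV need not be overstated.** A reader might infer that it is overstated whenever random biopsies miss anything. That also requires histology without false positives. The plan describes one reviewing pathologist and no second read, so f cannot be taken as zero, and step 6 shows that modest values change the sign.

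**Reversal is far-fetched.** Largely right. A reader might infer that the Pocket contrast could easily come out backwards, but at 0.60 vs 0.80 this needs, for example, r = 0.25 for VIA/VILI and 0.75 for Pocket. The Background links poor VIA performance to lesion size and lack of magnification. Lesions missed by the naked eye may therefore be the larger ones, and easier to hit at random, which points the other way.

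**The inputs are invented.** They are assumed, and shown as ranges. The directions in step 1 need only the stated inequalities and the no-false-positive condition. The sizes do rest on the assumptions. Taking 20% as true prevalence would be wrong, because the plan calls it a diagnosis rate.

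**The sample sizes may not apply.** Correct. The documents give 1056 and 400, end randomisation, and do not say how many women were randomised. The rejection rates describe an unpaired test, not the planned McNemar's test, which needs both results in the same woman.

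**Conclusion.** The concern holds in a bounded form. Reference quality depends on the index result and may differ by arm, and the plan makes no allowance for it. With test-positive meaning a lesion seen and no false-positive histology, sensitivity is overstated if r < d and NPV if r < 1. With equal d/r the order of the arms is safe but the size of the gap is not. With unequal d/r, a gap can appear where none exists: 11 points in the example, declared significant about half the time (49% to 57%) at an assumed 528 per arm.

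The documents do not show which arm is favoured, nor that the contrast is reversed. They also do not allow a Pocket advantage to be called conservative, or a null result to be read as equivalence. If some exam-negative women had directed biopsies, because the cut-off is stricter than any visible lesion, r moves towards d and the sensitivity bias falls.

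**What to change.** 1. For VIA/VILI vs Pocket, replace McNemar's test with an unpaired comparison of concurrently randomised women, and state how many there are. The 550 Pocket-only women do not enter it. McNemar's test remains suitable where two readings of the same woman's images are compared.
2. Beside sensitivity and specificity, report between-arm ratios with 95% CIs of the proportions of randomised women who are test-positive with, and without, biopsy-proven CIN2+. Describe the first as relative detection by exam plus biopsy. It is free of r, but equals relative sensitivity only if d is the same in both arms.
3. Define test-positive.
4. Add a sensitivity analysis of sensitivity, NPV and the arm contrast over arm-specific r (for example 0.25 to 0.75), d (0.7 to 1.0) and a small histology false-positive rate, calibrated to the observed diagnosed rate. State that absolute sensitivity and NPV are conditional on these values.
5. Label these analyses post hoc if the randomised data have already been compared.

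The cost is SAP wording and a small analysis of data already collected, with no further biopsies. The limits should be stated too. The detection ratio has low power (step 7) and is more exposed than the sensitivity comparison to arm differences in d. Neither measure dominates, so both should be shown. Absolute sensitivity and NPV are not fully repaired.

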Invasive cervical cancer (ICC) affects the lives of 500,000 women worldwide each year, resulting in more than 270,000 deaths [1]. Unlike most cancers, ICC is highly preventable through the screening, diagnosis and treatment of cervical precursor lesions [2]. The *Papanicolaou (Pap) smear*, a highly effective screening method available in most developed countries, is not generally available in low- and middle- income countries (LMICs) due to cost and infrastructure requirements. To address this disparity, the World Health Organization (WHO) recommends adoption of alternative protocols that employ low-cost or simple-to-use screening technologies and treat all women who are positive based on these tests [3]. One such screening strategy, human papillomavirus (HPV) testing, has been shown to reduce the incidence and mortality from cervical cancer when coupled directly with outpatient treatment (generally cryotherapy) for women with HPV-positive results [4]. However, recent guidelines have moved back from this "screen & treat" approach, given concerns about overtreatment [5]. The American Society of Clinical Oncology (ASCO) recently released guidelines recommending that HPV be used as a screening test, followed by triage with Visual Inspection with Acetic Acid (VIA) to confirm the presence of lesions prior to treatment.

VIA involves applying acetic acid to the cervix, examining the cervix with the naked eye, and making a diagnosis. While this may decrease the rate of overtreatment, VIA remains a poor triage test for the following reasons. VIA has high variability depending on provider experience, patient age, and size of lesion and has diminished sensitivity due to lack of magnification [2], [6]. Because there is no capability to capture images with VIA, there is no documentation to assess front-line health workers' performance, limiting quality monitoring and opportunities for skills improvement [7], [8]. Moreover, acetic acid enhancement lacks both sensitivity and specificity compared to the case in which it is combined with visualization of glycogen depletion and/or neovascularization [9]- [11]. In short, because VIA is not an effective triage solution for HPV+ women, there remains a crucial need for an appropriate second test that

is low-cost, easy-to-use and will identify, microscopic disease and at the same time, prevent overtreatment.

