The collaborating clinicians will identify subjects who are HPV+ and require visual inspection. The population will include those who are undergoing screening for the diagnosis of cervical cancer. The collaborating healthcare provider will introduce the study to potential subjects. The research team will explain the purpose and background of the study, the selection criteria, the subject's involvement, benefits, risks, compensation (for injury), costs, alternatives, confidentiality and disclosure issues with the patient. Informed written consent will be obtained from patients who are willing to participate at the time of the colposcopy visit. In addition to obtaining informed written consent, the patient's ethnicity and race will be collected. Finally, pathologic information, age, and BMI will also be obtained. A total of 400 patients will be recruited for the study.

Subject's Capacity to Give Legally Effective Consent

- If subjects who do not have the capacity to give legally effective consent are included, describe how diminished capacity will be assessed. Will a periodic reassessment occur? If so, when? Will the subject be consented if the decisional capacity improves?

Subjects who are not competent to give consent will not be included. Specifically, subjects who are not able to understand the consent form or the reasons why the study is being conducted will not be included. If the subject cannot read, the RA ([name]) has the option of reading the consent form to the subject aloud.

Study Interventions

- If not already presented in #4 above, describe study-related treatment or use of an investigational drug or biologic (with dosages), or device, or use of another form of intervention (i.e., either physical procedures or manipulation of the subject or the subject's environment) for research purposes.

The subject agrees to participate and signs the informed consent document. The subject will be randomized to either the standard of care visual inspection (VIA) arm OR the pocket-assisted visual inspection (PA-VIA) arm. The study scheme is described above in Figure 3. Once the procedure is complete, all subjects will have a follow-up phone call within 1 month to assess any post-procedural problems and/or adverse events. Once this occurs, the research procedures are considered complete.

Risk/Benefit Assessment

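### McNemar's test is planned for VIA/VILI against Pocket and against the algorithm, but each woman has only one type of exam, so these comparisons have no pairs

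*Combined protocol and SAP*

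**What the plan says.** Primary objective 1 (Purpose of the Study) is to compare the Pocket colposcope with VIA and VILI for detecting precancerous lesions in HPV-positive women. For the analysis, the plan states that "the two-sided McNemar's test will be used to determine statistically significant differences in specificity and sensitivity for each comparison 1) VIA/VILI impression" versus Pocket provider impression is comparison 1. Comparison 2 is expert reading versus algorithm. Comparison 3 sets both the VIA/VILI and the Pocket impressions against the algorithm. The same section specifies that the VIA/VILI impression is the standard-of-care one. It gives no other test.

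The design has parallel groups. Design & Procedures: "participants will be randomized 1:1 to either standard-of-care visual inspection or colposcopy with the Pocket Colposcope". Study Interventions repeats it: "The subject will be randomized to either the standard of care visual inspection (VIA) arm OR the pocket-assisted visual inspection (PA-VIA) arm". The standard-of-care exam is done with the naked eye. In the Pocket arm the acetic acid and iodine steps are both done with the device: "Using the Pocket Colposcope, images will be acquired and used to direct biopsy if a lesion is present". Cellphone images are also described only for women randomised to Pocket. Background & Significance gives as a drawback of VIA that images cannot be captured with it: "Because there is no capability to capture images with VIA".

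A later paragraph of Design & Procedures ends randomisation: "We plan to proceed with prospective enrollment of 550 subjects in the research arm only". It ties past and new images to the algorithm objective and does not mention comparison 1.

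**The concern.** McNemar's test works on the discordant cells of a table that cross-classifies two results from the same person. If no woman has both a naked-eye VIA/VILI result and a Pocket or algorithm result, that table is empty and the test does not exist. The analyst would then have to choose a method for the primary comparison after the data are in, which is what a prespecified plan should prevent.

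Two related points are open.

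- **Kappa.** The plan proposes standard and weighted kappa among three tests without naming them. If VIA/VILI is one of the three, kappa is undefined for every pair that includes it.
- **The 550 Pocket-only women.** The plan does not say whether they enter comparison 1. Including them would make a randomised comparison partly non-randomised.

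**Working it through.** **Step 1: count the pairs.** With 1056 women at 1:1 (Design & Procedures), each arm has 1056 / 2 = 528.

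| Comparison | Where each result comes from | Women with both |
|---|---|---|
| 1: VIA/VILI vs Pocket provider | standard-of-care arm; Pocket arm | 0 |
| 2: expert vs algorithm | both on Pocket images | up to 528 |
| 3a: VIA/VILI vs algorithm | standard-of-care arm; Pocket images | 0 |
| 3b: Pocket provider vs algorithm | both in Pocket arm | up to 528 |

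The 550 later women have the Pocket exam only, so they add no pairs to 1 or 3a. McNemar suits 2 and 3b.

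**Step 2: what an unpaired test could detect.** The plan states no power, alpha or effect size, so 1056 cannot be reproduced from its own inputs. From the plan: 1:1 allocation, two-sided testing and about 20% CIN2/3 in each arm. Assumed: alpha 5%, power 80%, baseline sensitivity 50-70%, baseline specificity 50-80%.

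- 1056 in total: 528 × 0.20 = 105.6, about 106 cases per arm; 528 × 0.80 = 422.4, about 422 non-cases.
- 400 in total (Subject Recruitment and Compensation: "A total of 400 patients will be recruited for the study"): 200 × 0.20 = 40 cases and 160 non-cases per arm.

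The number per arm, with p̄ = (p1 + p2)/2, is

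n = [1.960·√(2p̄(1−p̄)) + 0.842·√(p1(1−p1) + p2(1−p2))]² / (p2−p1)²

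Example, sensitivity 0.60 vs 0.777: p̄ = 0.6885, so n = [1.960·√0.4289 + 0.842·√0.4133]² / 0.177² = (1.284 + 0.541)² / 0.0313 ≈ 106.

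Solving for p2 gives these detectable gains, in percentage points:

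| Measure | Per arm | Baseline 50% | 60% | 70% | 80% |
|---|---|---|---|---|---|
| Sensitivity | 106 | 18.8 | 17.7 | 15.9 | – |
| Sensitivity | 40 | 29.5 | 27.2 | 23.8 | – |
| Specificity | 422 | 9.6 | 9.2 | 8.4 | 7.1 |
| Specificity | 160 | 15.4 | 14.6 | 13.2 | 11.0 |

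Exact binomial enumeration of the pooled z-test for sensitivity gives 18.8, 17.7 and 15.7 points with 106 per arm, and 29.4, 26.9 and 23.1 with 40.

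**Step 3: why unpaired power must be judged on its own.** Take sensitivity 60% vs 75%, a difference δ = 0.15. With n = 106 true pairs and discordant proportion s, McNemar power is Φ[(δ√n − 1.960√s)/√(s − δ²)].

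- s = 0.20: (1.544 − 0.877)/0.421 = 1.58, power 94%.
- s = 0.45 (independent readings): (1.544 − 1.315)/0.654 = 0.35, power 64%.

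The unpaired test with 106 per arm has 65%. A power figure worked out for correlated pairs would therefore be too optimistic here.

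**Step 4: the 550 Pocket-only women.** If pooled, the non-randomised share of the Pocket group would be 550 / (528 + 550) = 51%, or 550 / (200 + 550) = 73%.

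**The case against.** The best defence is that some pairing may exist outside the text reviewed. The study scheme (Figure 3) is not shown in it. Background & Significance also says that in routine Kenyan care women have a VIA assessment before treatment, so a Pocket-arm woman might also be looked at with the naked eye. Neither point restores the test. Nothing says that such an assessment is recorded as a study result, it would not supply VILI, and the either/or allocation is stated twice. Reading VIA/VILI as the Pocket-assisted steps fails too, because the analysis section specifies standard of care and the protocol labels the Pocket steps separately.

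Several narrower objections have weight.

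- The remark that VIA cannot capture images is background. The stronger support is that Design & Procedures describes images only for the Pocket arm.
- Kappa is valid if the three tests are the exam, expert and algorithm readings of the same Pocket images. That point is a request for clarification.
- No text proposes pooling the 550 women; the 51% and 73% show only what is at stake if someone did.
- The detectable gains describe the replacement test under assumed baselines. The size of the error itself is 0 pairs.
- Sensitivity, specificity and predictive values within each arm (primary objective 2) can still be estimated.
- An unpaired test leaves two separate matters open: each arm's exam directs its own biopsies, so disease ascertainment may differ by arm, and images used to develop the algorithm may also be used to test it. Changing the test neither creates nor worsens either one.

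**Conclusion.** The concern holds and needs correcting before analysis. Comparison 1 and the VIA/VILI half of comparison 3 have 0 pairs under the procedures described, so the only test stated for primary objective 1 cannot be carried out. Comparison 2 and Pocket provider versus algorithm are correctly paired.

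This conclusion rests on the text alone and on no assumed rate. The detectable gains do depend on the assumptions in Step 2 and on a total that the documents give as both 1056 and 400. The number actually randomised before the switch to Pocket-only enrolment is not stated. Whether the 550 women enter comparison 1, and which three tests kappa covers, are open questions rather than shown errors.

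**What to change.** 1. For comparison 1 and for VIA/VILI versus algorithm, replace McNemar with one prespecified unpaired comparison between the randomised arms. A suitable choice is the difference in proportions with a Miettinen-Nurminen score 95% confidence interval and its matching two-sided score test. Another method for independent proportions would also serve, provided it is fixed before analysis.
2. Compare the proportion test-positive among women with CIN2+ (sensitivity) and the proportion test-negative among women without it (specificity). Define the threshold: the analysis section mentions CIN2/3, while the pathology categories list invasive carcinoma separately.
3. Restrict this comparison to women randomised between the arms, state how many there were, and exclude the 550 Pocket-only women.
4. Keep McNemar for Pocket provider, expert and algorithm readings of the same woman.
5. Name the three tests for kappa and limit kappa to readings of the same woman.

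The cost is analysis wording only; no new data or visits are needed.
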